7.2.1 Analysis of Outcomes of Interest

The effects of the ATTOC model on provider adherence to guidelines for treating TUD: We hypothesize that the ATTOC intervention will increase adherence to guidelines for treating TUD vs. UC. The outcome is continuous and the hypothesis will be tested by a treatment arm term in a mixed-models linear regression model that may include covariates. Mixed models may account for individual level clustering inherent in longitudinal studies and site level clustering. Outcomes of the analysis will be characterized by regression coefficients and confidence intervals. Significance will be determined from a z-score corresponding to the treatment variable. Although level of adherence at 36 and 52 weeks will represent our primary outcome variables, similar regression analyses will be performed for assessments at Weeks 12 and 24. Also, we can examine models of specific clinician practices (e.g., identifying smoking, recommending pharmacotherapy) and examine adherence from the client perspective and based on adherence data ascertained from the EHR.

The effects of the ATTOC model on client smoking: The hypothesized effect of treatment arm (i.e., the difference in quit rates between subjects receiving the ATTOC intervention or UC) will be tested by a treatment arm term in a mixed-models logistic regression model with covariates. Outcomes of the analyses will be characterized by odds ratios (e.g., odds of quitting smoking) and 95% confidence intervals. Although quit-rates at the end of 36 and 52 weeks will represent our primary outcomes, similar analyses will be performed for other assessments of quit rates (e.g., at Weeks 12 and 24). In addition, as many participants will fail to become abstinent, we will explore the use of zero-truncated negative binomial regression for count data to examine the main effects of treatment arm on changes in smoking rate at all assessment time-points.

The effects of the ATTOC model on client mental health functioning and QOL: We will compare treatment arms in terms of the frequency of hospitalizations (binary) and mental functioning evaluations (continuous) over 52 weeks. Again, we will use mixed models to account for clustering, while accommodating either the binary outcome with logistic regression or the continuous measures with linear regression. Equivalence uses two one-sided tests against lower and upper equivalence bounds. The null hypothesis is that the groups are not equivalent and are determined to be equivalent when the mean or proportion is significantly different from both boundaries. We will use this approach to determine whether hospitalization rates are higher (null) in the ATTOC group or equivalent, and whether mental functioning is lower in the ATTOC group (the null) or equivalent. All hypotheses will be tested at $\alpha=0.05$ (0.025 for any one sided non-inferiority test).

The cost-effectiveness of the ATTOC program vs. UC: We will compare the societal cost (i.e., the sum of all measured categories of costs, including treatment and indirect costs) and effects of ATTOC vs. UC. If one treatment is found to be more costly and more effective, there is a trade-off between the additional effectiveness and additional resources needed to achieve those outcomes. This trade-off is represented by the incremental cost-effectiveness ratio (ICER), which is a ratio of the difference between mean costs in each treatment group and the difference between the cessation rates across treatment arms at weeks 36 and 52. This ratio will represent the additional cost of ATTOC vs. UC to produce an additional quitter. The quit rate outcome measure is used in our primary measure of cost-effectiveness because it is measured directly and because it can be compared against economic evaluations of other smoking interventions. Hypothesis testing for an ICER involves determining whether the ICER is significantly $<$ the maximum acceptable ICER. Unfortunately, the maximum willingness to pay for a quit is unknown. However, \$50,000 is accepted as a maximum ICER for the outcome of cost/life year saved, but wide bands around this value are common. This outcome looks at cost-effectiveness of the intervention over a lifetime. Because this is a relatively brief trial we will use a simulation-based analysis to project effects of quitting into long-term mortality and costs [116], employing standard assumptions and parameters [117]. Because this projection is based on parameters that have wide ranges, we will conduct a sensitivity analysis to assess the sensitivity of our estimates of costs and cost-effectiveness to the speculative nature of some of the values used in the analysis. We will consider how cost-effectiveness may change with different: 1) costs of treatment; 2) methods to handle attrition of cost data; and 3) ceiling ratios. Because of the poor statistical properties of the ICER as with ratios [118], we will transform the ratio into incremental net monetary benefits (INMB) with the following: $[L \cdot E] - C$ where L =ceiling ratio, E =difference in mean effects, and C =difference in mean costs. The hypothesis test that the ICER is $<$ the ceiling ratio is equivalent to the hypothesis test that the INMB is >0 . The INMB standard error is estimated with the formula in Willan [119] and amounts to the typical statistical formula for standard error. The hypothesis is that the ICER will be cost effective if the

INMB expression of cost/life year saved is >0 at an $\alpha < 0.05$. We will also judge the cost-effectiveness ratio as being acceptable if the confidence interval for the INMB excludes 0.

Exploratory Aims: The effects of treatment arm on potential mediators (barriers) will be assessed using linear regression-based structural equation modeling (SEM). It is hypothesized that treatment arm will yield significant differences in proposed mediators which will predict week 36 and 52 quit rates and adherence to treatment guidelines. We will examine changes in mediators from baseline to week 8. After first demonstrating that treatment arm affects adherence and quit rates (Aims 1 and 2), these effects will be partitioned into mediated and unmediated effects, via path analysis and SEM. Specific hypotheses will be tested by using chi-square difference tests that contrast the overall fit of this full model with more parsimonious nested models in which specific predictive effects are fixed to zero (e.g., an unmediated path). Model goodness-of-fit indices will be contrasted to guide interpretation of results and determine the practical significance of statistically significant differences. Modification indices will be examined to guide model interpretation and modification and binary and continuous variables can be handled by Stata. This approach allows us, in principle, to test whether treatment effects on Aim 1 and 2 outcomes are due to specific mechanisms (e.g., reduction in barriers).

Given the necessary complexity of the ATTOC intervention to promote broad, sustainable organizational change, we will use SEM to identify and measure the key elements of ATTOC related to improved outcomes (clinician behavior and client smoking) as has been suggested [18]. We will use the ATTOC Intervention Adherence Tool (i.e., "The Dashboard") to determine each site's compliance with ATTOC's steps (e.g., the selection of a site champion, the preparation of change and communication plans, the implementation of change plans including SOPs, the provision of TUD treatment, the establishment of a smoke-free campus or progress in establishing smoking restrictions). First, we can use SEM with binary predictors (e.g., identified a tobacco champion or not) to determine the relative impact of implementing each ATTOC element so that policy-makers can select a smaller, more manageable number of organizational change elements within ATTOC to implement; this may be especially relevant for disseminating ATTOC to sites which already successfully perform certain aspects of ATTOC already. Second, we can use SEM again to calculate the individual and combined impact of implementing ATTOC elements on outcomes, analogous to determining the "dose" effect of implementing various levels of ATTOC. These analyses will help policy-makers know the likely size of effects from implementing various ATTOC elements and make decisions about what their agency requires.

8 Safety and Adverse Events

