4.1 General Design

This cluster-randomized trial will be conducted with 14 Philadelphia CMHCs, 7 randomized to ATTOC and 7 to usual care (UC). Following randomization, study staff will visit sites to recruit clinic personnel and clients over a 4 to 6 week period. Those eligible will complete informed consent and HIPAA forms and a baseline assessment to establish pre-intervention levels on all measures (baseline). After 4-6 weeks, the ATTOC intervention will be implemented over 9 months, from Week 1 to Week 36 (with UC at the control sites). Two mid-intervention assessments (Weeks 12 and 24) will allow for performance feedback (see Outcomes Data) and mediational analyses. Week 36 (end-of-treatment; EOT) and 52 (3-months post-EOT) assessments will allow for evaluation of changes on outcomes between groups over time. All measures will be conducted at the respective CMHC

(or over the phone if necessary) and 7-day point prevalence smoking cessation will be verified using a breath carbon monoxide (CO) monitor (abstinence = < 8ppm; [93]). Figure 1 illustrates the study design.

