4.2 Randomization to Interventional Group

Although randomization and inclusion criteria will increase comparability between arms, sites will be matched by: 1) size (i.e., moderate [15-30 personnel; 110-249 clients] vs. large [>30 personnel; >249 clients]) 2) organizational motivation (e.g., < 30 vs. ≥ 30 on sum of all 12 items from the Organizational Readiness for Implementing Change [ORIC] measure [92]). We will try to enroll >2 sites (1/arm) that do not respond to initial invitations to enroll to include CMHCs with low readiness to implement change. Using the ORIC and outreach to sites with low motivation, we hope to reduce the potential of over-volunteering that can limit generalizability. If a CMHC has multiple locations, all locations will be randomized to the same arm but they will be considered 1 of the 14 randomized sites. Once eligible and interested sites are identified, using the small-sample equivalent to matching on stratification data, they are randomly assigned to UC or ATTOC. Computerized randomization within our Data Management System (DMS) will be provided by [name]. Once randomized, participants (personnel and clients) will be recruited for the trial.

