4.3 Rationale for Study Design

An alternative design would involve randomization of clients and providers within the agencies. Although that could avert potential confounds attributable to differences between agencies, we considered the risk of contamination – and, thus, a threat to internal validity – from such a design to be too probable. While an agency-level randomization may be subject to confounding as well, we will match the agencies on key variables before randomization to increase control over potential treatment confounds and we will use appropriate analytic models to account for this potential confounding (see Data Analysis). We also considered either: 1) not including a control arm; or 2) providing a more potent control arm, but considered the present design one that would allow for more convincing conclusions about the effects of ATTOC vs. current practice. Thus, we viewed the proposed design to be the ideal balance between internal and external validity.

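### No primary model names the two factors used to match clinics, so any precision gained from matching may go unrecognised in the linear analyses

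*Combined protocol and SAP*

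**What the plan says.** Section 4.1 allocates 14 clinics 7:7. In section 4.2, "sites will be matched by: 1) size" (moderate or large), and by organisational motivation, split at 30 "on sum of all 12 items from the Organizational Readiness for Implementing Change" measure. The mechanism is given only as "using the small-sample equivalent to matching on stratification data, they are randomly assigned to UC or ATTOC"; neither pairs nor strata are defined. Section 4.3 gives the purpose: "we will match the agencies on key variables before randomization to increase control over potential treatment confounds". It then adds that "we will use appropriate analytic models to account for this potential confounding (see Data Analysis").

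The analysis sections do not follow this through. Section 7.2 specifies random site effects within treatment. It lets variables associated with arm or with follow-up completion at p < .10 become covariates, without requiring it. In section 7.2.1 the Aim 1 hypothesis is "tested by a treatment arm term in a mixed-models linear regression model that may include covariates", with significance read from a z-score. The Aim 2 logistic model refers to covariates without naming them. The Aim 3 models mention clustering only. Size, ORIC, pair and stratum appear in none of these descriptions.

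**The concern.** When allocation is constrained on a prognostic clinic factor, that factor contributes little to the difference between arms. If the model omits it, its variance stays in the between-clinic error. The reported standard error then exceeds the true one, and power is lost.

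Between-clinic variance governs precision in this trial: the Aim 1 detectable difference in section 7.1 rises from 0.32 at ICC 0 to 0.62 at ICC .15. For the continuous Aim 3 outcomes, an interval that is too wide makes non-inferiority harder to show. Leaving the terms open also leaves a choice to the analyst, and with 14 clusters optional covariates can change the result.

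**Working it through.** **Inputs.** From sections 4.1 and 7.1: 14 clinics (7 per arm), 280 personnel (m = 20 per clinic, 140 per arm), SD 0.87, ICC 0 to .15, alpha .05 (taken as two-sided). Assumed, because the documents give no figure: R², the share of between-clinic variance explained by size and ORIC. Also assumed: four strata of 4, 4, 4 and 2 clinics, each split evenly between arms.

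**1. Reproduce the plan's figure.** Detectable difference = (t.975 + t.80 on 12 df) × √[2·SD²·(1 + (m − 1)·ICC)/140]. At ICC .10 this is (2.179 + 0.873) × √[2 × 0.7569 × 2.9/140] = 3.051 × 0.177 = 0.540. At ICC 0/.05/.10/.15 the formula gives 0.317/0.443/0.540/0.623, against the stated 0.32/0.44/0.54/0.62. The power plan therefore uses 12 df and the full ICC, and takes no credit for matching.

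**2. True standard error under exact balance (ICC .10).** Between-clinic variance is 0.10 × 0.7569 = 0.0757. The within-clinic part of a clinic mean is 0.90 × 0.7569/20 = 0.0341.
- R² = 0: √[2(0.0757 + 0.0341)/7] = 0.177.
- R² = 50%: √[2(0.0378 + 0.0341)/7] = 0.143.

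In 60,000 simulated null trials analysed on clinic means, the arm-only model at R² = 50% reported an average standard error of 0.182 against the true 0.143. At R² = 0 it was correct (0.177 for both).

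**3. Aim 1 detectable difference at 80% power (noncentral t).**

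| Model | ICC .05 | ICC .10 | ICC .15 |
|---|---|---|---|
| Arm only, 12 df | 0.443 | 0.541 | 0.623 |
| Arm + size + ORIC, 10 df, R² = 0 | 0.452 | 0.551 | 0.635 |
| same, R² = 10% | 0.440 | 0.531 | 0.609 |
| same, R² = 30% | 0.415 | 0.490 | 0.555 |
| same, R² = 50% | 0.389 | 0.446 | 0.496 |

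Adjustment gains once R² exceeds about 5-7%. With seven pair effects (6 df) the break-even is about 23-35%.

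**4. Simulated error rate and power, ICC .10, true difference 0.54 for power, exact balance.**

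| R² | Arm only: type I, t on 12 df | Arm only: type I, z | Power, arm only (t) | Power, adjusted (t on 10 df) |
|---|---|---|---|---|
| 0 | 5% | 7.4-7.9% | 80% | about 1.5 points lower |
| 25% | 3.0% | 4.8% | 81% | 86% |
| 50% | 1.3-1.5% | 2.4-2.6% | 82% | 92% |

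The adjusted t-test on 10 df holds about 5% throughout. Adding the factors but keeping z gives about 8% at every R² tried; referring a 10-df t statistic to ±1.96 gives 7.8% by direct calculation.

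**5. The p < .10 screen.** With 7 clinics per arm, a 5 against 2 split on a binary factor gives a clinic-level chi-square of 14 × (5·5 − 2·2)²/7⁴ = 2.57, p about .11. Even that imbalance would not pass, and factors matched by design should be closer than that.

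The simulations used equal clinic sizes and one variance for both arms. The separate variance components in section 7.2 were not modelled.

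**The case against.** Several stronger readings are tempting, and the documents do not support them.

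- **That the benefit of matching is lost.** The stated purpose is comparability and control of confounding. Balance survives an unadjusted model, and the estimate itself is still more precise (true standard error 0.143 rather than 0.177 in step 2).
- **That the standard errors are too wide as a matter of fact.** This needs R² above zero. The choice to match on these factors presumes they matter, but no figure is given, and at R² = 0 the standard error is correct.
- **That the planned test runs below its nominal level.** Section 7.2.1 uses a z-score for Aim 1. With 14 clinics that pushes the other way: 7.4-7.9% at R² = 0, about nominal at 25%, and conservative only when R² is larger.
- **That no primary model contains the factors.** The Aim 1 and Aim 2 wording leaves room for them. What can be said is that none names them.
- **That power is lost in all three aims.** Only a continuous outcome was examined. In the logistic models (Aim 2, hospitalisation) adjustment changes the conditional odds ratio and need not narrow its standard error.

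The objection on balance has force. Clinics are recruited prospectively (section 5.5) in groups of 3, 4, 4 and 3 (section 4.6), so exact balance within strata is not assured. In the limiting case of unrestricted 7:7 allocation at ICC .10, the arm-only t-test held 4.7-5.1% at every R². Adjusting then cost power at R² = 0 (about 79% to 70%) and gained nothing at R² = 25% (79.5% to 78.1%).

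The screen might also behave differently if run on individuals. A 4 against 3 split of clinics is 80/140 against 60/140 staff, giving chi-square 280 × (80·80 − 60·60)²/140⁴ = 5.7. Whether a factor enters would then depend on a level of testing that the plan does not state, which is a further reason to fix the terms in advance.

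**Conclusion.** The point holds in a limited form. The plan constrains randomisation on size and ORIC and promises models to match, but no primary model names either factor, and the optional screen is unlikely to bring in factors balanced by design.

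To the extent that the factors are prognostic and the arms well balanced on them, the arm-only linear models for Aim 1 and the continuous Aim 3 outcomes understate their own precision. At ICC .10 with a t reference, the Aim 1 power forgone is about 5 points at R² = 25% and about 10 points at R² = 50%. Both R² values are assumptions. The direction carries over to the continuous Aim 3 outcomes, but these figures were computed for Aim 1 only. For Aim 2 and hospitalisation, the reason to include the factors is consistency with the randomisation, not a narrower standard error.

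**What to change.** In section 7.2.1:

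1. State that the Aim 1-3 primary models include size stratum and ORIC as fixed clinic-level terms whatever their p-values. Fix in advance whether ORIC enters as the two-level split or as the 12-item sum; either uses one degree of freedom.
2. For the linear models, use a t reference on between-clinic degrees of freedom (14 − 2 − 2 = 10) in place of the Aim 1 z-score rule, and state the same reference for the continuous Aim 3 outcomes. Items 1 and 2 belong together, since adding the terms while keeping z gives about 8% type I error.
3. State in section 4.2 whether allocation was paired or stratified. Fit pair terms only if it was truly pairwise, since seven pairs leave 6 df.

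Both factors are already collected at clinic screening, so the change is one of wording. It uses 2 of 12 between-clinic df. If the factors are not prognostic, the cost is about 1-2 points of power under exact balance, and up to about 9 points in the limiting case of no balance at all.

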7.1 Sample Size and Power Determination

For cluster-randomized designs, clinic is the unit of randomization and the unit of analysis is the individual. Power is reduced by variability among clinics, represented by the intra-class correlation (ICC), analogous to an R-squared. The size of the individual sample affects precision within clusters and certain outcomes are less susceptible to potential confounding vs. others (e.g., smoking rates vs. provider adherence) since they are more independent.

For Aim 1, the analysis will compare ATTOC to UC on weeks 36 (EOT) and 52 rates of adherence to guidelines for treating TUD. The sample size was determined by assessing the mean change in practice behavior detected in Guldish et al. [18]. Given the expectation from that trial that the UC mean level of practice will be 2.36 (SD=.87), the present sample of N=14 agencies (with 280 subjects) provides 80% power ($\alpha=.05$) to detect an effect if practice behavior increases by 0.32 (on a 5-point scale) if the ICC is 0. But if our ICC is .05, .10, or as high as .15, we have 80% power ($\alpha=.05$) to detect a difference between ATTOC and UC of 0.44, 0.54, and 0.62, respectively. If 15% of the personnel are lost-to-follow-up, we will have 80% power ($\alpha=.05$) to detect an effect if practice behavior increases by 0.34 for ICC=0, by 0.46 for ICC=.05, by 0.56 if ICC=0.10, and by 0.63 if ICC=.15. The effects of ATTOC were stronger at the 3-month follow-up (mean change of 0.51), vs. EOT [18], so the current power is adequate for both time-points. Likewise, because the client sample will be more than twice as large as the clinic staff sample, we will have greater than 80% power to detect differences using the measure of physician adherence collected from clients.

For Aim 2, the analysis will compare the rates of smoking cessation between the ATTOC intervention and UC at weeks 36 and 52. We can expect that UC cessation rate will be < 2% [18]. With 14 sites (n=700 clients, ITT), we have 80% power ($\alpha=.05$) to detect a difference between ATTOC and UC of 4% with an ICC=0. But if our ICC is .05, .10, or as high as .15, we have 80% power ($\alpha=.05$) to detect a difference between ATTOC and UC of 10%, 15%, and 19%, respectively, with 14 sites and n=700 client (ITT).

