For Aim 3, the analysis will use non-inferiority testing to compare mental health and QOL across ATTOC and UC at weeks 36 and 52. Standard statistical tests, which may yield a non-significant comparison of means or proportions, cannot be used to claim that the treatments are equal since "the absence of evidence is not evidence of absence". Among persons with SMI, the rate of psychiatric hospitalization nationally is 11.4% [114], which may represent UC (i.e., 88.6% of UC subjects will not have a hospitalization across the 52 weeks). One study found that 3.3% of clients with an SMI treated for TUD had a psychiatric hospitalization [48] or that 96.7% of clients treated for TUD did not experience a psychiatric hospitalization. We assume 14 sites (700 clients), with potential loss of 15% to follow-up, and assume approximately 90% non-hospitalization in the UC group. We will set our non-inferiority floor 20% below the US rate, which yields 80% power to detect non-inferiority if the ICC is as much as 0.15 (more power if ICC is less than 0.015).

A trial with smokers with an SMI reported baseline BASIS-R scores of 2.1 (SD=0.8) and SF-12 scores of 48.7 (SD=12.5) for the physical sub-scale and 27.8 (SD=12.9) for the mental sub-scale, which estimates UC [107]. Given the sample of 14 sites (700

clients) and potential 15% loss to follow-up, we have 80% power ($\alpha=0.05$) to detect non-inferiority if the results for the ATTOC arm differ from UC by as much as 0.19 on the BASIS-R, when ICC=0, and by 0.50 when ICC=0.15.

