7.2 Statistical Methods

We will assess sample characteristics by treatment arm and site with chi-square or regression. These variables will also be examined for their relationship to completion of outcomes. Variables related to treatment arm or completion of follow-ups ($p < .10$) may be covariates in analyses. Fidelity and adherence measures will be evaluated across treatment arms, and the measures can be included in primary analyses. We will examine if the rate of missing data is related to a range of variables using chi-square and regression and use appropriate methods for dealing with missing data (e.g., [115]). Analyses will assume that all subjects for whom smoking outcome data are unavailable are smokers (ITT) but we can also conduct a "completers-only" analysis. Because this is a cluster-randomized trial, the observations within a cluster cannot be considered totally independent. Variation among clusters may be confounded with treatment because clusters are nested within treatment. We will account for this clustering using hierarchical linear models (mixed models), estimating separate variance components for random site effects within treatment. Lastly, since we cannot guarantee that clinicians will be blind to their clients enrolling in this study, we will include a statement in personnel consent forms asking that they refrain from asking their clients if they are enrolled in the study.

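### Aim 1 significance rests on a z-score with only 14 clinics and no small-sample correction; at the plan's ICCs of .05 to .15 the 5% test can run above its level, by an amount that depends on the estimator and on the matching

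*Combined protocol and SAP*

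**What the plan says.** Section 7.2.1 tests Aim 1 by the treatment term of a linear mixed model in which covariates are optional. It then states: "Significance will be determined from a z-score corresponding to the treatment variable". The same paragraph adds: "Outcomes of the analysis will be characterized by regression coefficients and confidence intervals". It gives neither the level nor the reference distribution of those intervals. Later in the section, alpha is set at 0.05 for all hypotheses, with 0.025 for one-sided non-inferiority tests.

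Section 4.1 randomizes 14 clinics, seven to each arm. Section 4.2 matches them on two two-level factors, size and organizational readiness. Section 7.2 handles clustering by "estimating separate variance components for random site effects within treatment", which could mean one site variance or one per arm.

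Section 7.1 sizes Aim 1 with 280 personnel and SD 0.87 at 80% power. It claims power "to detect an effect if practice behavior increases by 0.32 (on a 5-point scale) if the ICC is 0", and at ICC .05, .10 and .15 power "to detect a difference between ATTOC and UC of 0.44, 0.54, and 0.62, respectively". With 15% loss the differences are "by 0.34 for ICC=0, by 0.46 for ICC=.05, by 0.56 if ICC=0.10, and by 0.63 if ICC=.15".

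No section gives a t reference, a denominator-df method, a permutation test, or a choice between REML and ML. The one mention of small samples, in Section 4.2, concerns matching.

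**The concern.** A z reference treats the standard error as known. Here its dominant part, the between-clinic variance, is estimated from 14 clinics. A random site effect puts that variance into the model but does not account for how imprecisely it is estimated.

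On 12 degrees of freedom the two-sided 5% critical value is 2.18 rather than 1.96. A result with |z| between 1.96 and 2.18, that is a z-based p-value between .029 and .05, would be declared significant for a primary aim but would not be on 12 df. With the reference and the estimator both open, the choice could also be made after the data are seen.

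**Working it through.** **Inputs.** 14 clinics, 7 per arm (4.1); 280 personnel, so m = 20 per clinic, or 17 after 15% loss (7.1); SD 0.87 and ICC 0, .05, .10, .15 (7.1); 12-30 staff per site (5.2); two-sided alpha 0.05 (7.2.1).

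**Step 1: reproduce the plan's Aim 1 differences.** SE = 0.87 × √{2[1 + (m−1)ICC]/(7m)}. At m = 20 and ICC 0 this is 0.87 × √(2/140) = 0.104. The detectable difference is SE times the sum of two quantiles:

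- t on 12 df: 2.179 + 0.873 = 3.051, giving 0.317
- z: 1.960 + 0.842 = 2.802, giving 0.291
- z with one clinic per arm subtracted: replace 7 by 6 in the SE, giving 0.315

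| m | ICC | Stated | t, 12 df | t, 13 df | z, 6 per arm | plain z |
|---|---|---|---|---|---|---|
| 20 | 0 | 0.32 | .317 | .315 | .315 | .291 |
| 20 | .05 | 0.44 | .443 | .440 | .439 | .407 |
| 20 | .10 | 0.54 | .540 | .537 | .536 | .496 |
| 20 | .15 | 0.62 | .623 | .618 | .617 | .572 |
| 17 | 0 | 0.34 | .344 | .342 | .341 | .316 |
| 17 | .05 | 0.46 | .462 | .459 | .458 | .424 |
| 17 | .10 | 0.56 | .555 | .551 | .550 | .510 |
| 17 | .15 | 0.63 | .635 | .630 | .629 | .583 |

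The three small-sample columns all lie within 0.01 of the stated values. Plain z is 0.024 to 0.050 too low throughout; under z the stated differences would have 85-87% power, not 80%.

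**Step 2: type I error of |z| > 1.96, assuming matching explains no clinic variance.** Simulated random-intercept data with no effect and variance estimates floored at zero (REML / ML, %):

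| Setting | ICC .05 | ICC .10 | ICC .15 |
|---|---|---|---|
| Common site variance, m = 20 | 7.0 / 8.7 | 7.3 / 9.3 | 7.4 / 9.5 |
| Site variance per arm, m = 20 | 6.5 / 8.1 | 7.1 / 9.1 | 7.3 / 9.3 |
| Site variance per arm, m = 17 | 6.3 / 7.8 | 7.1 / 9.0 | 7.2 / 9.3 |
| Common site variance, clinics of 12-30 | 7.2 / 9.0 | 7.5 / 9.6 | 7.5 / 9.7 |

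At m = 20 with a common variance, ICC 0 gives about 4.0 / 4.5 and ICC .01 about 5.1 / 6.0. As a check, P(|t| > 1.96) on 12 df is 7.4%, the REML limit when the floor at zero plays no part.

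**Step 3: matching effective but left out of the model.** Seven matched pairs stand in for the strata, with m = 20 and a common variance. The share of clinic variance explained is an assumption, since the documents give none. Ranges are over ICC .05-.15.

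| Share | z, REML | z, ML | t on 12 df, REML |
|---|---|---|---|
| 0% | 6.9-7.4 | 8.6-9.5 | 4.6-5.0 |
| 10% | 6.3-6.5 | 8.0-8.4 | 4.2-4.3 |
| 20% | 5.5-5.7 | 7.2-7.3 | 3.6-3.7 |
| 30% | 4.6-5.1 | 6.1-6.5 | 2.9-3.2 |

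**Step 4: matching factors in the model.** Two two-level factors leave 14 − 2 − 2 = 10 df. P(|t| > 1.96) on 10 df is 7.8% for REML, and 12.9% for ML, again with no floor at zero. Inflation therefore returns.

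**Step 5: what the remedy needs.** At share 0%, ML with t on 12 df still gives about 6.0-6.6% at m = 20, so changing the reference without naming REML is not enough.

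**The case against.** The strongest reply is the matching. Clinics are matched before randomization, and covariates are optional. A model that omits effective matching factors overstates the standard error, which offsets the z reference; at a 30% share the REML test is close to nominal. This stands, and a reader who infers a fixed excess regardless of matching goes further than the documents allow. It does not rescue the rule: the offset rests on an unknown share, is incomplete under ML at every share tried, and disappears once the matching factors enter the model.

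It is also fair that under REML the excess is at most about 2.5 points, that there is none at ICC 0 (the first scenario in Section 7.1), and that the higher figures need ML, which the plan does not name.

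Two further inferences are tempting. One is that the plan was sized with a t distribution. Section 7.1 names none, and a normal formula with one clinic per arm subtracted fits about as well; only some small-sample allowance can be inferred. The other is that Aims 2 and 3 share the fault. The z-score sentence stands in the Aim 1 paragraph only, and nothing here shows an error in the other two analyses.

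**Conclusion.** The Aim 1 rule is wrong as written and should be changed. With 14 clinics, z is not the right reference for the treatment term, and nothing elsewhere in the plan corrects it. If matching explains no clinic variance, a nominal 5% test runs at about 6.3-7.5% (REML) or 7.8-9.7% (ML) at three of the four ICCs the plan lists. At an assumed 20% share left unadjusted, the figures are about 5.5-5.7% and 7.2-7.3%.

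The disagreement between sizing and test does not depend on matching: none of the eight Aim 1 differences fits plain z. The simulated rates are for one time-point with normal data and do not address testing at both week 36 and week 52.

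**What to change.** Replace the z-score sentence for Aim 1 with the following:

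- Fit by REML, and refer the treatment term to t on between-clinic degrees of freedom: Kenward-Roger or Satterthwaite, or a t-test on clinic summaries.
- Include the two matching factors and reduce the degrees of freedom to match, to about 10.
- Use the same reference for the Aim 1 confidence intervals, and state their level.
- Say whether Section 7.2 means one site variance or one per arm. If per arm, use Satterthwaite or an unequal-variance t-test on clinic means rather than a fixed df.
- Name the formula behind the Aim 1 differences in Section 7.1.

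**Cost.** This is wording and a software option. Intervals widen by about 11% against z on 12 df (2.179/1.960), or 14% on 10 df (2.228/1.960). The stated differences keep about 79-81% power on 12 df, or about 78-79% on 10 df before any precision gain from the matching factors. A fixed t on 12 df with a REML fit is conservative if the ICC is near 0 (2.3%) or if matching is effective but unadjusted (about 3-4%). With no matching effect, a t-test on clinic means holds 5.0% even at ICC 0.
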